17. SAFETY OUTCOMES

All safety assessments, including AEs, clinical laboratory evaluations, and vital signs will be listed and where appropriate summarized with descriptive statistics by treatment and scheduled visit/time point. Safety summaries will be provided for the following treatment group: Placebo Pooled (pooled from 2 dose groups), BI 730357 400 mg QD, BI 730357 300 mg BID, BI 730357 Pooled (pooled from 2 dose groups) and Ciprofloxacin 500 mg BID. All summaries for safety outcomes will be based on the treated set using the randomized treatment.

No statistical hypothesis testing is planned for safety data, unless otherwise specified with the relevant section.

Document: L:\BIOS\Boehringer_Ingelheim_Pharmaceuticals\BI730357\1407-0037_MZA56588\Biostatistics\Documentation\SAP

Author: [REDACTED] Version Number: Final V2.0
Version Date: 23JUL2020

Template No: CS_TP_BS016 – Revision 5
Effective Date: 01Apr2018

Reference: CS_WI_BS005

Copyright © 2009, 2010, 2012, 2016, 2018 [REDACTED] All Rights Reserved. The contents of this document are confidential and proprietary to [REDACTED] and its subsidiaries. Unauthorized use, disclosure or reproduction is strictly prohibited.

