Trial endpoints Trial design	 The primary endpoints are: Phototoxicity index at 24 h under condition 1 Phototoxicity index at 24 h under condition 2 The secondary endpoints are: Phototoxicity index at 10 min under condition 1 Phototoxicity index at 1 h under condition 1 Phototoxicity index at 10 min under condition 2 Phototoxicity index at 1 h under condition 2 Minimum Erythema Dose (MED) percent change from baseline at 10min, 1h, and 24h measured under condition 1 and condition 2 All endpoints are applicable for both treatment parts. This is a partially blind, randomized, parallel group, placebocontrolled study conducted in two treatment arms.
	Treatment Part A will be conducted according to a randomized,

BI Trial No.: 1407-0037

c27983101-03 Clinical Trial Protocol Page 3 of 79

	double blind, placebo-controlled design to assess the photosensitivity potential, safety, tolerability, and pharmacokinetics of multiple doses of BI 730357. Subjects will be randomized in a 3:1 manner to receive BI 730357 or placebo.
	Subjects will receive 400mg QD of BI 730357 or placebo over 8 days, or 300 mg BID of BI 730357 or placebo over 7 days with a single dose on day 8. Separate randomizations will be carried out for 400 mg QD/placebo and 300 mg BID/placebo.
	Photosensitivity assessments will occur at baseline and following the last dose of either BI 730357 or placebo.
	Treatment Part B will be conducted according to an open-label, observer-blinded design to assess the photosensitivity potential of ciprofloxacin (a mild photosensitizer) as a positive control.
	Subjects will receive 500 mg ciprofloxacin twice-daily starting on Day 3 through to the morning of Day 8.
	Photosensitivity assessments will occur at base line and following the last dose of ciprofloxacin.
Total number of subjects randomised	Approximately 84 subjects will be enrolled to allow for at least 74 completed subjects
Number of subjects on	36 subjects in Part A for 400 mg QD
each treatment	36 subjects in Part A 300 mg BID
	12 subjects in Part B
Diagnosis	Healthy volunteers
Main in- and exclusion criteria	Healthy male and female subjects as determined by past medical history, physical examination, vital signs, electrocardiogram, and laboratory tests at screening;
	aged ≥18 to ≤55 years, with a BMI range: ≥18 to ≤35 kg/m
	Fitzpatrick skin type I, II, or III
	Fitzpatrick Skin Type Description:
	I Always burns easily, never tans
	II Always burns easily, tans minimally
	III Burns moderately, tans gradually

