3.2 DISCUSSION OF TRIAL DESIGN, INCLUDING THE CHOICE OF CONTROL GROUP(S)

This is an approximately 8 weeks Phase I trial in healthy volunteers consisting of the two treatment parts.

The design of this clinical photosensitivity study followed the general concepts of ICH S10 (a recently published international guideline on "Photosafety Evaluation of Pharmaceuticals"), and included ciprofloxacin as a positive control (R19-2247).

Three distinct exposure conditions were included to account for seasonal and regional differences in human exposure to sunlight.

A two-layer randomization process will be employed:

Allocation to the Study part: Subjects will be randomly allocated to part A or part B in a 3:1 ratio in an open-label manner. Randomization numbers defining subject allocation to study part will be assigned in ascending, sequential order to eligible subjects.

Treatment Part A will be conducted according to a randomized, double blind, placebo-controlled design.

It is standard in trials involving healthy volunteers to include a placebo group as control for the evaluation of safety. Treatment Part A group will consist of 36 subjects in 400 mg QD group and 36 subjects in 300 mg BID group, with each group having 27 on active treatment and 9 on placebo.

The treatment will be blinded throughout the whole trial, to minimize any bias that could be introduced by knowledge of the treatment by either the investigator or the subject.

[figure not shown]
Treatment Part B will be conducted according to an open-label, observer-blinded design to assess the photosensitivity potential of ciprofloxacin (a mild photosensitizer) as a positive control.

c27983101-03 Clinical Trial Protocol Page 33 of 79

Proprietary confidential information © 2020 Boehringer Ingelheim International GmbH or one or more of its affiliated companies

12 subjects will receive 500 mg ciprofloxacin b.i.d. over 5 days with a single dose on the 6^{th} day.

The open-label treatment is not expected to bias the photosafety results, since the trial endpoints derived from the photosensitivity assessments will be provided by an observer performing skin evaluations which is blinded to treatment allocation.

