4.1.2 Selection of doses in the trial and dose modifications

The dose of 400 mg BI 730357 QD or 300 mg BID for this trial are selected on the basis of the PK and safety data obtained in the SRD and MRD trials 1407.0001 and 1407-0002, preliminary PK and safety data obtained in patients with plaque psoriasis in the ongoing 1407.30 study, combined with the preclinical data (see section 1.1), are intended to cover the highest therapeutic dose range (including safety margin) chosen for the future clinical development of BI 730357 in diverse indications.

In the SRD trial, single dose levels up to 800 mg and in the MRD trial, multiple dose levels up to 400 mg were well tolerated in healthy volunteers, and doses up to 200mg were well tolerated in plaque psoriasis patients.

Blinded photosafety data will be evaluated by the independent Investigator and BI medical team after completion of the 400 mg BI 730357 or placebo QD treatment.

If no photo-safety concerns have been observed in the Treatment A group,300 mg BI 730357 or placebo BID will be conducted.

The Ciprofloxacin dose selected in this trial reflects the standard clinical dose with acceptable safety profile. Ciprofloxacin was chosen as the positive control based on its property as mild photosensitizer (R 19-2246, R 19-3127).

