7.1 NULL AND ALTERNATIVE HYPOTHESES

BI 730357 vs placebo

The assessment for absence of photosensitivity will be based upon the differences in mean photosensitivity index (PI) between BI 730357 and placebo two-sided 90% confidence intervals (CIs) for the differences in the photosensitivity index (Section 7.2.2) between BI 730357 and placebo using an acceptance range of -0.4 to 0.4. This method is equivalent to the two-sided t-test procedure, each at the 5% significance level.

The following comparisons will be performed:

- BI 730357 400 mg QD vs placebo 400 mg QD
- BI 730357 300 mg BID vs placebo 300 mg BID

The following hypotheses are tested:

Null hypothesis H₀ (Photosensitive): $\mu_{BI} - \mu_{pbo} \le -\delta \ or \ \mu_{BI} - \mu_{pbo} \ge \delta$

Where μ_{BI} and μ_{pbo} are the means of the endpoint for BI 730357 and placebo, respectively, and δ is the limit that defines the acceptance range for photosensitivity equivalence.

Alternative hypothesis H_a (Absence of photsensitivity): $-\delta < \mu_{BI} - \mu_{pbo} < \delta$

In this trial, the equivalence limit δ is 0.4 which is consistent with historical criteria used for positive photosensitivity for a drug (R19-3037).

The rejection of the null hypothesis at the $\alpha = 0.05$ level is equivalent to the inclusion of the 90% confidence interval for μ_{BI} - μ_{pbo} in the acceptance range (- δ , δ).

Although there are multiple endpoints where the photosensitivity index will be statistically compared, an alpha adjustment is not needed because it is required that all endpoints meet the equivalence criterion as described above simultaneously.

c27983101-03 Clinical Trial Protocol Page 63 of 79

Proprietary confidential information © 2020 Boehringer Ingelheim International GmbH or one or more of its affiliated companies

BI 730357 vs ciprofloxacin, Placebo vs ciprofloxacin

Comparisons between the mean PI between BI 730357 and ciprofloxacin as well as between placebo and ciprofloxacin at the different timepoints under conditions 1 and 2 will be performed.

The planned comparisons are:

- BI 730357 400 mg QD vs ciprofloxicin
- BI 730357 300 mg BID vs ciprofloxicin
- Placebo for 400 mg QD vs ciprofloxicin
- Placebo for 300 mg BID vs ciprofloxicin

At each timepoint the null hypothesis will be that there is no difference in the mean PI of BI 730357 compared to ciprofloxacin:

Null hypothesis H_0 : $\mu_{BI/pbo} - \mu_{cipro} = 0$

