6.2. TREATMENT SUMMARIZATION

In general, data will be presented for each treatment group (BI 730357 400 mg QD, Placebo QD, BI 730357 300 mg BID, Placebo BID and ciprofloxacin 500 mg BID). Data for subjects in the following combined treatment groups will also be presented when appropriate:

- All subjects combined, presented as Overall
- All BI 730357 treated subjects combined from the 2 dose groups, presented as BI 730357 Pooled
- All placebo treated subjects combined from the 2 dose groups, presented as Placebo Pooled

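### SAP 17 tabulates each single-dose safety column beside pooled placebo only; the placebo subjects randomised with that dose should have their own column

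*SAP*

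**What the plan says.** SAP 17 sets the columns for all safety summaries: "Safety summaries will be provided for the following treatment group: Placebo Pooled (pooled from 2 dose groups"), followed by the two BI 730357 regimens separately, BI 730357 pooled, and ciprofloxacin. The active doses stay apart and the placebo groups do not.

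Elsewhere the SAP treats the placebo groups differently. SAP 6.2 sets the default: "In general, data will be presented for each treatment group (BI 730357 400 mg QD, Placebo QD, BI 730357 300 mg BID, Placebo BID", with ciprofloxacin as the fifth group. It then adds pooled groups as extras: "Data for subjects in the following combined treatment groups will also be presented when appropriate". The treatment-group table in SAP Appendix 1 lists Placebo QD and Placebo BID for tables, graphs and listings, and has no pooled placebo entry.

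On design, the Protocol Synopsis states: "Separate randomizations will be carried out for 400 mg QD/placebo and 300 mg BID/placebo". Protocol 3.2 describes the two Part A cohorts of 36 "with each group having 27 on active treatment and 9 on placebo". The cohorts are sequential. Protocol 4.1.2 says "Blinded photosafety data will be evaluated by the independent Investigator and BI medical team after completion of the 400 mg BI 730357 or placebo QD", and the 300 mg BID cohort follows if that review raises no concern. SAP 3.1 has the two cohorts enrolled under protocol Versions 1.0 and 3.0. SAP 14 counts 8 placebo doses in one cohort and 15 in the other.

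Protocol 7.2.5 makes safety descriptive, without hypothesis tests, and does not mention pooling placebo. SAP 17 gives no reason for it.

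**The concern.** Within each cohort, randomisation makes placebo a fair control for that cohort's active dose. A pooled placebo column beside a single-dose column loses part of that protection, because half of its planned subjects were never randomised with the dose. They were treated at another time and on another placebo schedule. They also had a different sampling load: Protocol Tables 10.2:1 and 10.2:2 give 18 against 22 PK draws, of which 2 against 9 fall on Day 1. Protocol 1.4.2 names mild bruising and, rarely, vein inflammation as risks of sampling.

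What is at stake is the reading of the single-dose columns. If background adverse-event or laboratory findings differ between cohorts for any reason, one dose looks somewhat worse against placebo than it is and the other somewhat better. The summary tables would not show the within-cohort comparison that is free of this. Protocol 7.2.5 says treatment groups will be compared descriptively on laboratory data, and a descriptive comparison can be confounded too.

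**Working it through.** **1. Planned counts.** Each Part A cohort has 36 subjects at 3:1. Active: 36 × 3/4 = 27. Placebo: 36 × 1/4 = 9. This reproduces Protocol 3.2. Pooled placebo: 9 + 9 = 18. Share from the other cohort: 9/18 = 50%.

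**2. Bias of a single-dose contrast.** Let b_QD and b_BID be the background rates in the two cohorts. With 9 placebo subjects each, the pooled column estimates (b_QD + b_BID)/2. With no drug effect:

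- 400 mg QD minus Placebo Pooled = b_QD − (b_QD + b_BID)/2 = (b_QD − b_BID)/2
- 300 mg BID minus Placebo Pooled = (b_BID − b_QD)/2
- BI Pooled minus Placebo Pooled = (27·b_QD + 27·b_BID)/54 − (b_QD + b_BID)/2 = 0

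The documents give no background rate for either cohort, so the rates below are assumptions.

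| b_QD | b_BID | Placebo Pooled | 400 mg QD minus pooled | 300 mg BID minus pooled | BI Pooled minus pooled |
|---|---|---|---|---|---|
| 20% | 20% | 20% | 0 | 0 | 0 |
| 20% | 40% | 30% | −10 points | +10 points | 0 |
| 10% | 30% | 20% | −10 points | +10 points | 0 |
| 10% | 50% | 30% | −20 points | +20 points | 0 |

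**3. Gap between the doses.** The pooled column is common to both doses and cancels: (BI 400 − Placebo Pooled) − (BI 300 − Placebo Pooled) = BI 400 − BI 300. Pooling leaves this gap unchanged.

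**4. Precision.** Take SE = √[p(1 − p)(1/n₁ + 1/n₂)], with p the same in both groups and assumed to be 20%:

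- own placebo, 27 v 9: √[0.16 × (1/27 + 1/9)] = 15.4 points
- pooled placebo, 27 v 18: √[0.16 × (1/27 + 1/18)] = 12.2 points

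With no placebo events, the upper two-sided 95% exact limit is 1 − 0.025^(1/n), which is 33.6% for n = 9 and 18.5% for n = 18.

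**5. Break-even.** Pooling has the larger mean squared error only when its squared bias exceeds the variance it saves: p(1 − p)(1/9 − 1/18) = 0.16 × 1/18 = 0.00889, whose square root is 9.4 points. The bias is half the cohort difference, so break-even is a cohort difference of about 19 points. The same sum gives about 14 points at p = 10% and about 24 at p = 50%.

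**The case against.** The strongest reply is that pooling is a sensible trade of bias for variance. Nine placebo subjects per cohort are few. By the break-even above, a cohort difference of 10 points would favour pooling at an assumed 20% rate, and 20 points is close to even. Both cohorts share one site, the same eligibility criteria, the same irradiation and residence days and the same follow-up, so a large difference is not obviously likely. Four more blood draws would hardly produce one. All of this stands, and it is why the pooled column should stay. It does not justify leaving out the randomised columns, since the tables can carry both.

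A second reply is that SAP 6.2 states only a general rule, that SAP 17 is the specific one, and that the table templates mentioned in SAP 8 are not in the public documents. That is fair as far as it goes. But SAP 6.2 offers pooled groups in addition, whereas SAP 17 uses one as a replacement without giving a reason, and Appendix 1 lists the two placebo groups for tables.

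Three stronger readings are tempting, and the documents do not support them:

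- A reader might infer that the plan promised own-placebo safety contrasts, from comparisons such as "BI 730357 300 mg BID vs placebo 300 mg BID" in Protocol 7.1 and their counterparts in SAP 15.3. Those concern the photosensitivity index only.
- A reader might infer that pooling creates or hides a difference between the two doses. It cannot, because the common column cancels. The gap between doses is a non-randomised comparison whether or not placebo is pooled. Correcting it through each cohort's placebo would be noisy: at an assumed 20% rate the SE is √[0.16 × (2/27 + 2/9)] = 21.8 points, against √[0.16 × 2/27] = 10.9 for the direct difference.
- A reader might infer that the within-cohort placebo data are lost. SAP 17 lists all safety assessments, and Appendix 1 orders listings by randomised group with the two placebo groups apart. Only the summary tables omit them.

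**Conclusion.** The point holds as a matter of presentation. In the SAP 17 summaries, each single-dose column is shown beside a placebo column of which a planned 50% comes from the other cohort, and this departs from the default in SAP 6.2 and the groups in Appendix 1. The distortion is half the cohort difference in background rate, with opposite signs for the two doses. Its actual size is unknown and may be zero. The 50% share assumes that planned numbers are met; replacements or drop-outs could shift it slightly.

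The consequence is modest. Safety is descriptive, BI Pooled against Placebo Pooled is balanced by cohort at the planned 3:1 ratio, and the photosensitivity analyses already use each cohort's own placebo. This is a cheap improvement and not a flaw that threatens the trial's conclusions.

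**What to change.** In SAP 17, add Placebo QD beside BI 730357 400 mg QD and Placebo BID beside BI 730357 300 mg BID in the safety summaries. Keep Placebo Pooled and state that it is to be read mainly against BI 730357 Pooled. This also reconciles SAP 17 with SAP 6.2 and Appendix 1. Make the change before unblinding.

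The cost is two more columns per table, built from groups the SAP already defines, with no new data and no change to trial conduct. The downside is wider tables and own-cohort contrasts that rest on 9 placebo subjects and are less precise, which is the reason to keep the pooled column as well.

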17.1. ADVERSE EVENTS

An AE is defined as any untoward medical occurrence in a patient or clinical investigation subject administered a medicinal product and which does not necessarily have to have a causal relationship with this treatment. An AE can therefore be any unfavorable and unintended sign (including an abnormal laboratory finding), symptom, or disease temporally associated with the use of a medicinal product, whether or not considered related to the medicinal product.

Protocol-specified Adverse Events of Special Interest (AESI) and infection AEs are identified on the eCRF by the investigator.

All adverse events with an onset between start of study medication and 7 days after the last dose study medication (i.e., end of the residual effect period [REP]) will be assigned to the on-treatment period for evaluation and considered as on-treatment AEs. Only on treatment AEs are considered for the summary of adverse events. Adverse Events (AEs) will be coded using MedDRA.

Treatment-emergent adverse events (TEAEs) are defined as AEs occurring between start of study medication and 7 days after the last dose study medication (i.e., end of the REP) inclusive. Adverse events that start before first study medication intake and deteriorate under treatment will also be considered as 'treatment-emergent'.

Pretreatment AEs are defined as AEs occurring prior to dosing. These events will be presented in the listings only and are not included in the tabular summary of AEs.

See APPENDIX 2 for handling of partial dates for AEs. In the rare case where it is not possible to assess treatment emergence, the AE will be classified as treatment emergent (i.e. the worst case).

Intensity (Severity)

The AE intensity is classified as mild/moderate/severe. TEAEs starting after the first dose of study medication with a missing severity will be classified as severe for analysis purposes. If a subject reports a TEAE more than once within that system organ class (SOC)/preferred term (PT), the AE with the worst case severity will be used in the corresponding severity summaries.

Causal Relationship to Study Medication

Relationship to study medication, as indicated by the Investigator, is classified as "related" or "not related". TEAEs with a missing relationship to study medication will be regarded as "related" to study medication for analysis purposes. If a subject reports the same AE more than once within that SOC/PT, the AE with the strongest case relationship to study medication will be used in the corresponding relationship summaries.

As an overview incidence summary of TEAEs, number and percentage of subjects with TEAEs, treatment-related TEAEs, mild TEAEs, moderate TEAEs, severe TEAEs, serious TEAEs, treatment-related serious TEAEs, Non-serious TEAEs, AESIs. TEAEs leading to study medication discontinuation, TEAEs leading to death and treatment-related TEAEs leading death will be presented by treatment.

Document: L:\BIOS\Boehringer_Ingelheim_Pharmaceuticals\BI730357\1407-0037_MZA56588\Biostatistics\Documentation\SAP

Author: [REDACTED] Version Number: Final V2.0
Version Date: 23JUL2020

Template No: CS_TP_BS016 – Revision 5
Effective Date: 01Apr2018

Reference: CS_WI_BS005

Incidence summaries, including number of events will be presented by SOC and PT for each treatment for the following:

- Overview summary across SOC and PT
- All TEAEs
- TEAEs by causal relationship
- All TEAEs by intensity
- All treatment-related TEAEs by intensity
- Non-serious TEAEs with incidence in preferred terms strictly greater than 5% in at least one of treatment groups.

17.1.1. TEAEs LEADING TO DISCONTINUATION OF STUDY MEDICATION

Treatment-emergent AEs leading to permanent discontinuation of study medication are those TEAEs with response to action taken trial drug due to AE reported as “Drug Withdrawn” on the Adverse Events page of the eCRF.

Treatment-emergent AEs leading to permanent discontinuation of study medication will be listed and summarized using an incidence table by SOC, and PT for each treatment.

17.1.2. SERIOUS ADVERSE EVENTS

Serious adverse events (SAEs) are those events recorded as “Serious” on the Adverse Events page of the eCRF, and will be listed. An incidence summary of serious TEAEs by SOC, and PT for each treatment will be prepared.

Non-serious TEAEs with incidence in preferred terms strictly greater than 5% in at least one of treatment groups will be summarized by SOC, and PT for each treatment.

17.1.3. ADVERSE EVENTS OF SPECIAL INTEREST

The following AEs will be recorded as Adverse Events of Special Interest (AESIs) in this trial:

Hepatic Injury

Hepatic injury defined by the following alterations of liver parameters (for subjects with normal liver function at baseline):

- An elevation of aspartate aminotransferase (AST) and/or alanine aminotransferase (ALT) ≥ 3 times the upper limit of normal (ULN) combined with an elevation of bilirubin ≥ 2 times ULN measured in the same blood draw sample;

Document: L:\BIOS\Boehringer_Ingelheim_Pharmaceuticals\BI730357\1407-0037_MZA56588\Biostatistics\Documentation\SAP

Author: [REDACTED] Version Number: Final V2.0
Version Date: 23JUL2020

Template No: CS_TP_BS016 – Revision 5
Effective Date: 01Apr2018

Reference: CS_WI_BS005

- Aminotransferase (ALT, and/or AST) elevations ≥ 10 fold ULN.

Severe infections

Opportunistic and mycobacterium tuberculosis infections

These include pneumocystis jirovecii, BK virus disease including PVAN, CMV, posttransplant lymphoproliferative disorder (EBV), progressive multifocal leucoencephalopathy, bartonellosis (disseminated only), blastomycosis, toxoplasmosis, coccidioidomycosis, histoplasmosis, aspergillosis (invasive only), candidiasis (invasive or pharyngeal), cryptococcosis, other invasive fungi (mucormycosis (zygomycosis, rhizopus, mucor, lichtheimia), scedosporium/pseudallescheria boydii, fusarium), legionellosis, listeria monocytogenes (invasive only), tuberculosis, nocardiosis, non-tuberculous mycobacterium, salmonellosis (invasive only), HBV reactivation, herpes simplex (invasive only), herpes zoster, strongyloides (hyperinfection syndrome and disseminated forms only), paracoccidioides, penicillium marneffei, sporothrix schenckii, cryptosporidium species (chronic only), microsporidiosis, leishmaniasis (visceral only), trypanosoma cruzi infection (Chagas' disease) (disseminated only), campylobacteriosis (invasive only), shigellosis (invasive only), vibriosis (invasive due to vibrio vulnificus), HCV progression.

The AESIs are those TEAEs with YES response to the question, "Adverse Event of Special Interest? "on the AE page of the eCRF and will be flagged in listing.

Incidence summaries by SOC and PT will be prepared for each treatment for the following:

- All AEs of hepatic injury
- All AEs of hepatic injury by severity
- All severe infections according to RCTC grading
- All opportunistic and mycobacterium tuberculosis infections
- All opportunistic and mycobacterium tuberculosis infections by severity.

A summary of the number of subjects, percentages, and number of events within will be provided by SOC, PT, and treatment for all treatment-emergent AESI, TEAEs of hepatic injury AESI, infection AESI, serious infection AESI.

